## Introduction

Background and rationale

6a

Pediatric concussion is a significant public health burden, sometimes referred to as a silent epidemic. More than a million children in North America sustain a concussion annually, and the numbers seeking medical care are rising dramatically. Children with concussion often report postconcussive symptoms, including somatic (e.g., headache, dizziness), cognitive (e.g., inattention, forgetfulness), and affective (e.g., irritability, dysphoria) complaints. Postconcussive symptoms are most severe acutely, but can persist for weeks to months and result in functional disability and declines in quality of life in 15-25% of children with concussion.

Multiple evidence-based clinical practice guidelines (CPGs) have been developed to guide the management of concussion in children. However, the implementation of CPGs in clinical settings is spotty, resulting in significant practice variation and knowledge gaps. For instance, among 577 front-line primary care providers in Ontario (i.e., family physicians, emergency medicine physicians, general pediatricians, nurse practitioners, and physician assistants) who diagnose and manage concussion, only 47% recommended an initial period of school absence, only 37% correctly applied return-to-play guidelines, and only 26% reported regular use of standardized rating scales for assessing concussion. Even among emergency medicine physicians from academic medical centers belonging to the Pediatric Emergency Research Canada network, only 64% correctly applied return-to-play guidelines, 60% recommended school absence, and 22% reported regular use of standardized rating scales for assessing concussion.

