The CP has grown out of the work of the MNCY SCN workgroup on pediatric concussion. It includes several elements, including diagnostic and prognostic tools, discharge instruction forms, information leaflets, and access to an informational website and for patients and parents. To develop the CP, the workgroup reviewed the existing CPGs for concussion diagnosis and management, and generated a "clinical knowledge topic" document that provides AHS practitioners with information and guidance about concussion care, including care pathways and algorithms. The CP originally incorporated tools such as the Acute Concussion Evaluation (ACE) for identification and diagnosis, the PECARN rule for determining the need for CT scan, and the 5P rule for predicting risk of persistent symptoms. The CP also was intended to include a parent/patient handout developed by the workgroup and approved by AHS. The CP for the study will be based on the most up-to-date evidence and consensus guidelines, as reviewed by the MNCY SCN pediatric concussion workgroup. Although the CP is not expected to change during the study period, it certainly could evolve over time as the evidence base for concussion increases, and consensus guidelines are updated. The goal is to reduce practice variation and improve care by using a CP to align acute diagnosis and management with evidence-based CPGs.

Qualitative interviews and site visits led to iterative changes in the CP to account for practice variations between sites and to enhance clinician buy-in. Initially the ACE tool was chosen as the primary CP tool for physician assessment; however, physicians felt that the ACE overlapped too much with existing assessments and did not direct patient care. Based on this feedback, the 5P rule scoring rubric was chosen instead of the ACE. The 5P risk score was implemented to enable automatic referrals of children at high risk of persistent postconcussive symptoms to a specialty concussion clinic, and also to encourage referral of low and medium risk children for follow-up by primary care providers.

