As shown in Table 3 on the next page, we have planned a comprehensive evaluation of both process and clinical outcomes to fulfill our second objective. Clinical outcomes will include four patient-centered outcomes, and process outcomes will include five measures of adherence to the CP (e.g., physician provision of discharge instructions; patient/parent adherence to key interventions as recommended by the CP). Physicians and nurses in the ED will distribute a concussion handout at discharge. The front page will advise the family to go to the RECOVER web portal for more information, and the last 4 pages will provide concussion education and advice, including about return to learn and return to play. Prior to CP implementation, the website will provide parents with tools to help track recovery; after CP implementation, it will also supply evidence-based information about how to promote recovery and obtain appropriate concussion care. Both prior to and after CP implementation, the website interface will ask patients and parents to rate their satisfaction with their care in the ED within 3 days of their visit, as well as their comprehension of and adherence to physician discharge recommendations, including those regarding return to school and return to play. They also will report on whether they perceive the patient to have returned to pre-injury status, and provide ratings of the patient's post-concussive symptoms and quality of life. Parents and patients will be blinded to site allocation. They will be able to provide their responses anonymously, or they can elect to provide informed consent to enable us to link their responses on the website to identifying information and medical data.

12b The primary outcome will be the time to symptom resolution based on weekly reports of whether the patient has returned to pre-injury status. Secondary patient-centered outcomes will include ratings of satisfaction with ED care and post-injury ratings of post-concussive symptoms and quality of life. The latter two outcomes will be assessed using the Health and Behaviour Inventory and the PedsQL, both of which are measures included in the NIH Common Data Elements for pediatric traumatic brain injury (see Surveys and Questionnaires in appendices).

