Secondary outcomes also will include measures of physician adherence, the number of unique website hits per IP address, the proportion of patient- and parent-reported adherence to physician discharge recommendations, the proportion of diagnosed concussions per visit (predicted to increase as physicians identify and code the injuries correctly), and the proportion of CT scans ordered per diagnosed concussion (predicted to decrease because the CP will include prediction rules for CT scanning in concussion).

12c *Table 3: Process and clinical outcomes*

| Outcome measure      | Description         | Details  |
|-----------------------------|----------------------------|---|
| Primary clinical outcome    | Time to symptom resolution | Weekly ratings by patients and parents of whether patient has returned to pre-injury status   |
| Secondary clinical outcomes | Postconcussive symptoms    | Weekly ratings on Health and Behaviour Inventory  |
|                             | Quality of life            | Weekly ratings on PedsQL  |
|                             | Satisfaction with care     | Post-visit rating of overall satisfaction with acute care   |
| Primary process outcome     | Physician adherence        | Proportion of completed discharge forms per diagnosed concussion    |
| Secondary process outcomes  | Patient/parent adherence   | Proportion of patient and parent reports of adherence to physician discharge recommendations involving rest, return to school, and return to play |
|                             | Patient/parent adherence   | Number of unique website hits per IP address  |
|                             | Physician adherence        | Proportion of diagnosed concussions per visit   |
|                             | Physician adherence        | Proportion of CT scans ordered per diagnosed concussion   |

Qualitative interviews and site surveys resulted in the discharge form being replaced by the 5P risk score sticker. To assess adherence, the study team recorded the number of 5P assessments completed by each site over the course of data collection.

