Statistical methods 19a Statistical analyses will involve comparisons of primary and secondary outcomes prior to versus after CP implementation. Children will fall into either the pre-CP or post-CP group because their care (including the version of the website and text messaging they receive) will be based strictly on when they present for acute care (i.e., prior to or after CP implementation at their respective site). Time to symptom resolution will be the primary outcome, and will be examined using survival analyses. First, Kaplan Meier estimates of the curves will be created, to obtain crude comparisons; Cox proportional hazards models will then be used to adjust for other variables. Apart from reporting hazard ratios, we also will present median time to symptom resolution (if reached) for pre- versus post-CP implementation. Other outcomes will be examined using mixed models with random effects for cluster, to adjust for clustering by site, and fixed effects for the test of CP status (pre/post implementation). Linear models will be used for continuous outcomes, Poisson for counts, and logistic regression models for binary outcomes. Exploratory analyses will examine whether the impact of implementation changes as sites gain more experience with the CP, by including the amount of time since the CP was implemented as a fixed effect in the model. Similarly, heterogeneity in intervention effects will be explored using testing interactions of CP status (pre/post) with site.

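### Patient/parent adherence is scored against the physician's own advice, which the pathway is meant to change, so pre- and post-implementation families are held to different benchmarks

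*Protocol*

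**What the plan says.** The protocol gives two reference standards for patient/parent adherence.

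- **The CP.** Item 12a presents the five process outcomes as measures of adherence to the CP and gives as an example "patient/parent adherence to key interventions as recommended by the CP".
- **The physician.** Table 3 (item 12c) defines the outcome as "Proportion of patient and parent reports of adherence to physician discharge recommendations involving rest, return to school, and return to play". The running text of item 12b agrees: "the proportion of patient- and parent-reported adherence to physician discharge recommendations". The portal question in item 12a, put to families before and after implementation, also refers to the physician. It asks for satisfaction with care, "as well as their comprehension of and adherence to physician discharge recommendations, including those regarding return to school and return to play".

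Two further statements bear on the difference. The Introduction says of the pathway: "The goal is to reduce practice variation and improve care by using a CP to align acute diagnosis and management with evidence-based CPGs". Item 6a reports how often the relevant advice was given without a pathway. Among Ontario front-line providers, "only 47% recommended an initial period of school absence, only 37% correctly applied return-to-play guidelines"; among academic emergency physicians, "only 64% correctly applied return-to-play guidelines, 60% recommended school absence".

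Item 19a compares outcomes before and after implementation, with a random effect for site and a fixed effect for CP status: "Linear models will be used for continuous outcomes, Poisson for counts, and logistic regression models for binary outcomes". It gives no rule for a family that received no recommendation.

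**The concern.** The intervention acts on the advice, and the outcome is scored against the advice. Before crossover, a family told something that departs from the guidelines is adherent if it does as told. After crossover, a family given CP advice is adherent only if it follows that advice. The two phases are measured with different rulers, and the pre/post term and site effect in item 19a cannot correct a difference built into the definition.

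Objective 2 asks whether implementation leads to uptake of the pathway. The other process outcomes are physician adherence (now counted through 5P assessments), website hits, diagnoses per visit and CT scans per diagnosis. None of them records whether families rest or return to school and play as the CP recommends. If this outcome misses a real change in behaviour, nothing else in Table 3 shows it directly.

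**Working it through.** The protocol states no rate, effect size or power for this outcome, so there is no figure to reproduce. The check is an illustration.

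**Inputs**
- *a* = share of families given CP-concordant advice. For the control phase, item 6a offers 37%, 47%, 60% and 64%. These are shares of surveyed physicians, not of families at the trial sites. Post-implementation values of 90% and 95% are assumptions.
- *f* = share of those families who follow the advice, equal in both phases. Assumed 60% to 80%.
- *g* = share of the remaining families who show the CP behaviour anyway, equal in both phases. Assumed 0% to 50%.

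**Step 1: the Table 3 measure under three codings.** Families without CP advice are treated as one group, with *a* rising from 47% to 90% and *f* = 70%.

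| Coding of families without CP advice | Formula | Before | After | Difference |
|---|---|---|---|---|
| Dropped | f | 70% | 70% | 0 |
| Counted adherent | a·f + (1 − a) | 0.329 + 0.53 = 85.9% | 0.63 + 0.10 = 73.0% | −12.9 points |
| Counted non-adherent | a·f | 0.47 × 0.70 = 32.9% | 0.90 × 0.70 = 63.0% | +30.1 points |

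Under the first coding the denominators also differ, at 47% of respondents before and 90% after.

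With control *a* from 37% to 64%, post-CP *a* = 90% and *f* from 60% to 80%, the codings give:
- dropped: 0 throughout;
- counted adherent: a fall of (0.90 − a)(1 − f), from 0.26 × 0.20 = 5 points to 0.53 × 0.40 = 21 points;
- counted non-adherent: a rise of (0.90 − a)·f, from 0.26 × 0.60 = 16 points to 0.53 × 0.80 = 42 points.

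**Step 2: scoring against the CP in all respondents.** The proportion is a·f + (1 − a)·g, so the change is (a₁ − a₀)(f − g). Take *a* from 60% to 95% and *f* = 80%:
- g = 0: 48% vs 76%, so 0.35 × 0.80 = 28 points;
- g = 20%: 0.48 + 0.40 × 0.20 = 56% vs 0.76 + 0.05 × 0.20 = 77%, so 21 points;
- g = 50%: 0.48 + 0.40 × 0.50 = 68% vs 0.76 + 0.05 × 0.50 = 78.5%, so 10.5 points.

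Over the Step 1 ranges with g from 0% to 20%, the rise runs from 0.26 × 0.40 = 10 points to 0.53 × 0.80 = 42 points. It stays positive whenever the CP raises *a* and advised families behave concordantly more often than others (f > g).

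**The case against.** Adherence to the advice a family actually received is a legitimate construct, and most of the protocol's wording uses it consistently. The CP-referenced phrase is a parenthetical example. Item branching and the coding of families with no advice are often settled in a questionnaire or analysis plan, and neither is in the text available here. This stands as far as coding goes. It does not remove the conflict over the reference standard, which the protocol itself fixes, nor the fact that a control family following non-CP advice is adherent by definition.

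A reader might infer more than the documents support:

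- **That unadvised control families are dropped or counted as adherent**, so that the measure necessarily conditions on something that happens after exposure. The protocol sets no such rule. If they are coded non-adherent, the measure with *a* from 60% to 95% and *f* = 80% is 48% vs 76%, and the effect is visible.
- **That the measure misses 28 points.** That size requires that no unadvised family behaves concordantly.
- **That the portal already records what children did.** Item 12a says only that it asks about comprehension of, and adherence to, physician recommendations.

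The contrast may also be smaller than illustrated. Item 12a describes a discharge handout with return-to-learn and return-to-play advice without tying it to a phase, although Table 2 (item 11c) lists a family handout as an implementation component. If control families receive it, the gap in advice narrows.

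**Conclusion.** The concern holds in this form: the protocol names two reference standards, the operative one shifts with exposure, and scoring is unstated for families given no advice. Depending on that scoring, the outcome can show no effect (70% vs 70%), a reversed effect (85.9% vs 73.0%) or a positive one (32.9% vs 63.0%) under one set of assumed rates. A CP-referenced measure would rise by 28, 21 or 10.5 points when 0%, 20% or 50% of unadvised families behave concordantly, given advice rising from 60% to 95% and 80% following it. These sizes rest on assumed post-implementation and follow-through rates and on physician-survey figures for the control phase, so they show direction and range and do not predict a result.

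The importance is moderate. This is one of four secondary process outcomes. It might be read as undermining the trial's main result, but the primary outcome is time to symptom resolution and does not depend on it.

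**What to change.** Reconcile item 12a with item 12b and Table 3 as follows:

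1. Define the outcome as the proportion of all portal respondents, in both phases, whose reported rest, return to school and return to play match the CP's own recommendations, whatever the emergency physician advised.
2. Report separately, over the same denominator, the proportion who say they received each recommendation.
3. Keep adherence to advice actually received as a descriptive measure, and state how families with no recommendation are handled in it.
4. State whether families receive the discharge handout before implementation.

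**Cost.** The change needs new wording in 12b and Table 3, a scoring rule taken from the CP itself, and possibly reworded portal items that ask what the child did. Any reworded items must be the same in both phases. Absolute adherence figures will be lower than under the present definition. The Table 3 footnote is in the past tense, which suggests that data collection may already have begun. If the items can no longer be changed, the three codings in Step 1 should be reported side by side and the outcome should not be read as a measure of pathway uptake.

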Health care utilization and costs associated with care of concussion will be compared before and after the implementation of the CP. Utilization and costs are expected to remain stable or decline following implementation of the CP.

*Overview.* The project will involve a stepped wedge cluster randomised trial to evaluate the implementation of the MNCY CP for the acute care of pediatric concussion. Stepped wedge designs randomise the sequence in which participating sites receive the study intervention, so that each site serves as its own control, but each site starts the intervention at a different time. Data collection continues throughout, so that each site contributes observations during both pre-intervention and post-intervention periods. In this case, each of four participating sites will be considered clusters, and they will be randomised to implement the MNCY CP over 11 months (i.e., after a 2 month lead-in period, implementation will occur at one site and then at the other three sites every 2 months, until implementation has occurred at all four sites, with data continuing to be collected 2 months after the CP is implemented at all sites).

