12d *Health care utilization.* We will assess the impact of the implementation of the CP on health care utilization using data from the National Ambulatory Care Reporting System (NACRS). Relevant outcomes will include acute care length of stay and return visits within 72 hours following acute care discharge. Appropriate procedures will be used to link administrative and health data. Use of NACRS data allows efficient capture of return visits, regardless of whether the patient returns to the index site. We will also use administrative data from AHS to assess health care utilization for pediatric patients with concussion. For each concussion diagnosed at the target sites, we will track the duration of stay in the ED, number of subsequent outpatient visits, and number of referrals to other health care services.

*Healthcare costs.* Payer costs associated with acute care for pediatric patients with concussion will be accounted for, based on ED visits, return visits, and physician fees, as well as subsequent outpatient care, which will be determined from the AHS administrative database. Costs for ED visits will be based on standard methodologies using resource intensity weightings (RIWs). Physician fees associated with ED and outpatient visits, including those for laboratory and diagnostic imaging services, will be captured through associated AHS billings. Cost data will be presented in Canadian dollars for the standard price year of 2014.

Participant timeline 13a *Project phases.* As shown in the Project Timeline below, the project will be divided into four phases. During the pre-implementation phase, which will last 12 months, we will complete site visits and key informant interviews, develop the intervention strategy, seek site approvals for the planned intervention, conduct a launch meeting, and complete randomization. The implementation phase will take place over the next 10 months. According to the stepped wedge design, data collection will occur continuously from 2 months prior to implementation at any site until 2 months after the CP is implemented at all four sites. Data collection will include the monitoring of outcomes, which are described below, during the course of the stepped wedge trial, which will last about 10 months.

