The third phase of the project will involve data analysis, which is expected to take 6 months. The final phase will involve dissemination of the study findings to all study sites and associated stakeholders, as well as to broader clinical and scientific audiences through conference presentations and journal publications. Within the context of the broader MNCY concussion workgroup, we also will begin planning for the scaling up of CP implementation on a province-wide level. The complete study is expected to take 3 years.

13b

| Project Activity               | Project Year |   |   |   |   |   |
|--------------------------------|--------------|---|---|---|---|---|
|                                | 1            |   | 2 |   | 3 |   |
| Hire & train personnel         | ■            |   |   |   |   |   |
| Pre-implementation             |              |   |   |   |   |   |
| Project site visits            | ■            | ■ |   |   |   |   |
| Key informant interviews       | ■            | ■ |   |   |   |   |
| Intervention mapping & design  |              | ■ |   |   |   |   |
| Site approvals                 |              | ■ |   |   |   |   |
| Launch meeting & site training |              | ■ |   |   |   |   |
| Randomization                  |              | ■ |   |   |   |   |
| Implementation                 |              |   |   |   |   |   |
| Collect data                   |              | ■ | ■ | ■ |   |   |
| Data analysis                  |              |   |   |   | ■ |   |
| Dissemination                  |              |   |   |   |   |   |
| Study site presentations       |              |   |   |   |   | ■ |
| Stakeholder presentations      |              |   |   |   |   | ■ |
| Conference presentations       |              |   |   |   |   | ■ |
| Journal publications           |              |   |   |   |   | ■ |
| Plan implementation            |              |   |   |   |   | ■ |

Sample size

14

*Analysis Strategy.* Characteristics of patients and sites will be summarized by exposure status (i.e., control versus intervention) to allow for consideration of possible selection biases. Relevant comparisons will include the number of pediatric patients with concussion at each site before and after the implementation of the CP, site characteristics such as total patient volume, and important patient characteristics, including age and sex.

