*Power calculation.* Power calculations for the primary outcome, time to symptom resolution, were computed using standard methods for two-group survival analyses (i.e., children who received care before versus after implementation of the CP). We conservatively assumed a sample size of 1,575, based on a total of 2,100 concussions per year across sites, a 50% rate of web site usage, and 18 months of recruitment. If we assume equal numbers of cases in the pre- and post-implementation phases, a median time to symptom resolution of 4 weeks, non-informative censoring because follow up will continue for 3 months, and no clustering effects, then the minimum hazard ratio that we can detect with .80 power at a significance level of .05 would be 1.20, which would represent at 20% higher likelihood of symptom resolution at any given time post-injury after implementation of the CP. Analyses will treat the randomised crossover from control to intervention as having occurred at the planned time, irrespective of any delays in actual implementation of the intervention, although secondary analyses will explore the effects of the actual timing of the crossover should any delays occur. All sites have provided written commitment to the study. Therefore, barring exceptional circumstances, no sites will be lost to follow-up.

Randomization

15

A study statistician will use a computerized algorithm to select a randomly generated order of implementation for the four sites.

Recruitment 16 Recruitment will rely on ongoing support and communication with clinicians. To avoid having implementation become stalled or displaced by other priorities, we will conduct monthly teleconferences with site champions to discuss progress and sustainability. Teleconferences will allow sites to discuss best practices and local solutions to common barriers. Additionally, the study coordinator and PI will be available for more informal consultation by email or phone.

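### The sample size of 1,575 assumes 18 months of recruitment, but the protocol describes a trial of 10 or 11 months, and the stated detectable hazard ratio of 1.20 fits neither duration

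*Protocol*

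**What the plan says.** Item 14 (Sample size, Power calculation) derives 1,575 children from "a total of 2,100 concussions per year across sites, a 50% rate of web site usage, and 18 months of recruitment". It assumes equal numbers before and after implementation, a median of 4 weeks to symptom resolution, and "non-informative censoring because follow up will continue for 3 months". The result is stated as "no clustering effects, then the minimum hazard ratio that we can detect with .80 power at a significance level of .05 would be 1.20".

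Other sections give different durations:

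- **Item 13a (Participant timeline):** "During the pre-implementation phase, which will last 12 months", then "The implementation phase will take place over the next 10 months", and again "the stepped wedge trial, which will last about 10 months". Data collection runs from 2 months before the first site implements until 2 months after the last.
- **Introduction, Overview:** "they will be randomised to implement the MNCY CP over 11 months", followed by a schedule of a 2-month lead-in, sites 2 months apart, and 2 months after the last site.
- **Item 13b (timeline chart):** the data-collection row is marked in three columns. With two columns per project year, these are the second half of year 1 and all of year 2. The next column is marked for data analysis, and item 13 describes "data analysis, which is expected to take 6 months".

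**The concern.** This calculation is the protocol's only justification of trial size. Accrual is a rate multiplied by time, so the sample stands or falls with the recruitment period. If the trial recruits for 10 or 11 months, the sample is far smaller than the one used and the stated detectable effect cannot be relied on. If 18 months is intended, the Overview and item 13a misstate how long the trial runs. As written, a reader cannot tell whether about 875 or 1,575 children are expected, and a null result could not be judged against a known detectable effect.

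**Working it through.** **Inputs.** From item 14: 2,100 concussions a year, 50% web site use, 18 months, equal groups, median 4 weeks, 3 months of follow-up, hazard ratio (HR) 1.20, significance level .05. From item 13a: 10 months. From the Overview: 11 months. Assumed because not stated: exponential recovery, the 4-week median applies before implementation, 3 months is 13 weeks, two-sided test, no loss.

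**Sample size.**
- 18 months: 2,100 × 0.5 × 18/12 = 1,575. The protocol's figure reproduces.
- 10 months: 2,100 × 0.5 × 10/12 = 875, a reduction of 1 − 875/1,575 = 44%.
- 11 months: 2,100 × 0.5 × 11/12 = 962.5, taken as 963, a reduction of 39%.
- The Overview's own steps: 2 + 3 × 2 + 2 = 10 months, not 11.

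**Chart.** The shaded columns are months 7 to 24. Eighteen months of recruitment fits only if it starts in month 7, inside the 12-month pre-implementation phase and in the half-year marked for site approvals and randomization. The last child's follow-up would end at 6 + 18 + 3 = month 27, in the half-year marked for analysis. Item 13a does not fit the shading either: 12 + 10 + 3 = month 25.

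**Events.** The probability of resolution within 13 weeks is 1 − 2^(−13/4) = 0.895 before implementation and 1 − 2^(−1.2 × 13/4) = 0.933 after, with mean 0.914.

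**Power.** Power = Φ(ln 1.2 × √(events/4) − 1.96). Detectable HR at 80% power = exp(2 × 2.8016/√events).

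| N | Events, no loss | Power at HR 1.20 | Detectable HR | Power (detectable HR) if 60% have observed events |
|---|---|---|---|---|
| 875 | 800 | 73% | 1.22 | 55% (1.28) |
| 963 | 880 | 77% | 1.21 | 59% (1.26) |
| 1,575 | 1,439 | 93% | 1.16 | 80% (1.20) |

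**Why 1.20 does not match 1,575.** Detecting 1.20 with 80% power needs (2 × 2.8016/ln 1.2)² = 945 events, and 945/1,575 = 60%. The last column applies that back-solved rate. The protocol states no such rate, although item 17b lets families stop entering data at any time.

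**Sensitivity.**
- One-sided .05, no loss: 82%, 86% and 97% (detectable HR 1.19, 1.18 and 1.14), so 1.20 still does not match 1,575.
- If 25% (assumed) of the 1,517 unspecified head injuries in item 9 were recoded as concussion: (2,100 + 0.25 × 1,517) × 0.5 × 10/12 = 1,033 children and about 80% power.

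**Calendar period, as illustration only.** In a stepped wedge, implementation status is tied to calendar time. With four equal sites and five periods, the share of sites that have implemented is 0, ¼, ½, ¾ and 1. The mean within-period variance of status is then (0 + 0.1875 + 0.25 + 0.1875 + 0)/5 = 0.125, against 0.25 unadjusted. Replacing events/4 with events × 0.125 gives 45% (N = 875) and 48% (N = 963). Using item 9 emergency department volumes as a proxy for site size (92,000, 50,000, and an assumed even split of 18,000), the variance is 0.068 to 0.138 over all 24 orders. Power is then 27% to 48% (N = 875) and 29% to 52% (N = 963).

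**The case against.** The strongest reply is that the conflict is one of wording and its effect is modest. Against the stated 1.20, the detectable hazard ratio moves only to 1.21 or 1.22. A one-sided test gives more than 80% power, and some recoding of unspecified head injuries, which item 10 contemplates, would restore 80%. If every child resolved within follow-up, power would be 77% or 81%. Item 14 names no formula beyond standard methods, so 73% or 77% comes from an assumed calculation. No enrolment cap depends on 1,575, and the chart could support 18 months as the intended window.

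Three parts of this stand. The protocol does not show which duration is intended, so the shortfall is conditional on the shorter readings. The 60% event rate is back-solved: 12 months of accrual (1,050 children, no loss) would explain 1.20 about as well, with 80.6% power. Item 14 openly declares that it ignores clustering, and the role of calendar period in the primary model may be settled in an analysis plan that is not shown, so the period-adjusted figures remain illustrations.

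The rest does not remove the point. The small shift in hazard ratio appears only when a no-loss result is set beside a stated figure that the no-loss calculation does not reproduce. Like for like, power falls from 93% to 73% or 77%, or from 80% to 55% or 59%. The chart fits 18 months only by overriding item 13a.

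**Conclusion.** The concern holds and must be fixed. The conflict between 10, 11 and 18 months is in the protocol's own text and needs no assumption. On the 10- or 11-month reading, the chance of missing a true hazard ratio of 1.20 is about 23% to 27% with no loss, against the stated 20%. It would be 41% to 45% if only 60% of children had observed events. These sizes rest on two-sided testing, exponential recovery and the item 14 accrual rate. Separately, 1,575 children, a hazard ratio of 1.20 and 80% power do not belong together on the stated assumptions, whether the test is one- or two-sided. Adjustment for calendar period would lower power further, by an amount that depends on the primary model, site sizes and between-site variance.

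**What to change.** 1. Reconcile the duration across the Overview and items 13a, 13b and 14, and say whether follow-up of the last child falls inside the data-collection window.
2. Restate the sample size for that window on S06.0 cases: about 875 for 10 months or 963 for 11. Keep 1,575 only if 18 months of recruitment is intended and the other sections are changed to match. State any recoding of S09.9 cases that is assumed.
3. Replace the item 14 result with a recomputed detectable hazard ratio, or power at 1.20, stating sidedness, event rate and loss.
4. Base that figure on the planned primary model, allowing for site and calendar period, and show it as a range over site sizes and between-site variance. The figures above illustrate such a range and are not proposed as protocol text.

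The cost is protocol wording and one recalculation. No extra enrolment is needed, though the restated figure may be less favourable.
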